Trial Summary Report

Date: 05/31/2023

Record Verification Date: 03/17/2023

Trial Identification	
Trial Category	Complete
Trial Type	Interventional
NCI Trial Identifier	NCI-2019-07902
Other Trial Identifiers	
Lead Organization Identifier	ADVL18P1
ClinicalTrials.gov Identifier	NCT04203316
DCP Identifier	No Data Available
CTEP Identifier	ADVL18P1
CCR Identifier	No Data Available
Amendment Number	4
Amendment Date	12/15/2022

General Trial Details	
Type	Interventional
Official Title	An Open-Label Feasibility Study to Assess the Safety and Pharmacokinetics of Enasidenib in Pediatric Patients with Relapsed/Refractory Acute Myeloid Leukemia (R/R-AML) with an Isocitrate Dehydrogenase-2 (IDH2) Mutation
Brief Title	Enasidenib for the Treatment of Relapsed or Refractory Acute Myeloid Leukemia Patients with an IDH2 Mutation
Acronym	No Data Available
Brief Summary	

This trial studies the side effects of enasidenib and to see how well it works in treating patients with acute myeloid leukemia that has come back after treatment (relapsed) or has been difficult to treat with chemotherapy (refractory). Patients must also have a specific genetic change, also called a mutation, in a protein called IDH2. Enasidenib may stop the growth of cancer cells by blocking the mutated IDH2 protein, which is needed for cell growth.
	
Detailed Description	

PRIMARY OBJECTIVES:
 
I. To determine the safety of treatment with enasidenib mesylate (enasidenib) administered at continuous daily oral dosing for a 28-day cycle up to 12 cycles in pediatric patients with IDH2-mutant relapsed/refractory (R/R)-acute myeloid leukemia (AML).
 
II. To characterize the plasma pharmacokinetic (PK) profile of enasidenib in pediatric patients with IDH2-mutant R/R-AML.
 
SECONDARY OBJECTIVES:
 
I. To investigate the pharmacodynamic (PD) relationship of oncogenic metabolite
	

2-hydroxyglutarate (2-HG) to enasidenib treatment in pediatric patients with IDH2-mutant R/R-AML.

II. To describe the clinical activity of enasidenib in pediatric patients with IDH2-mutant R/R-AML.

OUTLINE:

Patients receive enasidenib orally (PO) once daily (QD) on days 1-28. Treatment repeats every 28 days for up to 12 cycles in the absence of disease progression or unacceptable toxicity. Patients also undergo bone marrow aspiration and/or biopsy and collection of blood on study.

After completion of study treatment, patients are followed up at 30 days, then periodically up to 1 year.

Sponsor	Children's Oncology Group
Lead Organization	Children's Oncology Group
Principal Investigator	[name]
Responsible Party	Sponsor
Overall Official	[name] (Principal Investigator), Children's Oncology Group

Status/Dates	
Current Trial Status	Active as of 01/30/2023
Trial Start Date	03/30/2020-Actual
Primary Completion Date	12/31/2030-Anticipated
Trial Completion Date	12/31/2030-Anticipated

Regulatory Information	
Studies a U.S. FDA-regulated Drug Product	No Data Available
Studies a U.S. FDA-regulated Device Product	No Data Available
Product Exported from the U.S	No Data Available
FDA Regulated Intervention?	Yes
Section 801?	Yes
DMC Appointed?	No
IND/IDE Study?	Yes

Human Subject Safety	
Board Approval Status	Submitted, approved
Board Approval Number	12/15/2022

IND/IDE						
Type	Grantor	Number	Holder Type	Holder	Availability of Expanded Access	Expanded Access Record
IND	CDER	146610	Organization		Unknown	

NIH Grants			
Funding Mechanism	NIH Institution Code	Serial Number	NCI Division/Program Code
U10	CA	180886	CTEP

Data Table 4 Information	
Funding Category	National
Funding Sponsor/Source	Children's Oncology Group
Anatomic Site Code	
Myeloid and Monocytic Leukemia	

Collaborators	
Name	Role
National Cancer Institute	Funding Source

Disease/Condition
Name
Recurrent Acute Myeloid Leukemia
Refractory Acute Myeloid Leukemia

Trial Design	
Type	Interventional
Primary Purpose	Treatment
Pragmatic Trial	No
Phase	II
Pilot Study?	No
Interventional Study Model	Single Group
Model Description	No Data Available
Number of Arms	1
Masking	No Masking
Masking Description	No Data Available

Allocation	NA
Target Enrollment	10

Eligibility Criteria

Accepts Healthy Volunteers?	No
Sex	All
Minimum Age	24 Months
Maximum Age	21 Years

Inclusion Criteria

- Patients must be ≥ 24 months and < 21 years of age at the time of study enrollment
- Patient must have AML with an IDH2 mutation identified from a peripheral blood or bone marrow sample at the time of diagnosis and/or relapsed/refractory disease
- Patient must have bone marrow assessment (aspiration or biopsy) with $> 5\%$ leukemic blasts by morphology and/or flow cytometry in at least one of the following clinical scenarios:
 - * Second or greater relapse after chemotherapy or hematopoietic stem cell transplant (HSCT)
 - * Refractory after ≥ 2 attempts at induction therapy
- Relapsed patients
 - * Must not have received prior re-induction therapy for this relapse
 - * Each block of chemotherapy (i.e., cytarabine, daunorubicin and etoposide [ADE], cytarabine and mitoxantrone [MA]) is a separate re-induction attempt
 - * Donor lymphocyte infusion (DLI) is considered a re-induction attempt
- Refractory patients
 - * Each attempt at induction therapy may include up to two chemotherapy courses
- Karnofsky $\geq 50\%$ for patients > 16 years of age and Lansky ≥ 50 for patients ≤ 16 years of age. Patients who are unable to walk because of paralysis, but who are up in a wheelchair, will be considered ambulatory for the purpose of assessing the performance score
- Patient's current disease state must be one for which there is no known curative therapy or therapy proven to prolong survival with an acceptable quality of life
- Evaluation of cerebrospinal fluid (CSF) is only required if there is a clinical suspicion of central nervous system (CNS) involvement by leukemia during eligibility screening. Should a patient be found to have CNS2 or CNS3 status by CSF prior to eligibility screening, patient may receive intrathecal chemotherapy > 72 hours prior to starting study drug. CNS1 status must be established before starting study drug
- Patients must have fully recovered from the acute toxic effects of all prior anti-cancer therapy and must meet the following minimum duration from prior anti-cancer directed therapy prior to enrollment. If after the required timeframe, the numerical eligibility criteria are met, e.g., blood count criteria, the patient is considered to have recovered adequately
 - * Cytotoxic chemotherapy or other anti-cancer agents known to be myelosuppressive. The duration of this interval must be discussed with the study chair and the study-assigned research coordinator prior to enrollment
 - ** ≥ 14 days must have elapsed after the completion of other cytotoxic therapy with the exception of hydroxyurea. Additionally, patients must have fully recovered from all acute toxic effects of prior therapy. NOTE: Cytoreduction with hydroxyurea must be discontinued ≥ 24 hours prior to the start of protocol therapy
 - ** Intrathecal chemotherapy must be completed ≥ 72 hours prior to the start of the first cycle of treatment
 - * Anti-cancer agents not known to be myelosuppressive (e.g. not associated with reduced platelet or absolute neutrophil count [ANC] counts): ≥ 7 days after the last dose of agent. The duration of this interval must be discussed with the study chair and the study-assigned research coordinator prior to enrollment

- * Antibodies: ≥ 21 days must have elapsed from infusion of last dose of antibody, and toxicity related to prior antibody therapy must be recovered to grade ≤ 1
- * Corticosteroids: If used to modify immune adverse events related to prior therapy, ≥ 14 days must have elapsed since last dose of corticosteroid
- * Hematopoietic growth factors: ≥ 14 days after the last dose of a long-acting growth factor (e.g., pegfilgrastim) or 7 days for short-acting growth factor. For agents that have known adverse events occurring beyond 7 days after administration, this period must be extended beyond the time during which adverse events are known to occur. The duration of this interval must be discussed with the study chair and the study research coordinator
- * Interleukins, interferons and cytokines (other than hematopoietic growth factors): ≥ 21 days after the completion of interleukins, interferon or cytokines (other than hematopoietic growth factors)
- * Stem cell Infusions (with or without total body irradiation [TBI]):
 - ** Allogeneic (non-autologous) bone marrow or stem cell transplant, or any stem cell infusion including donor lymphocyte infusion (DLI) or boost infusion:
 - *** ≥ 60 days after infusion for bone marrow or stem cell transplant and
 - *** ≥ 4 weeks after infusion for any stem cell infusion including DLI or boost infusion
 - *** There must be no evidence of graft versus host disease (GVHD)
 - ** Autologous stem cell infusion including boost infusion: ≥ 42 days
- * Cellular Therapy: ≥ 42 days after the completion of any type of cellular therapy (e.g. modified T cells, natural killer [NK] cells, dendritic cells, etc.)
- * XRT/external beam irradiation including protons: ≥ 14 days after local XRT; ≥ 150 days after TBI, craniospinal XRT or if radiation to $\geq 50\%$ of the pelvis; ≥ 42 days if other substantial bone marrow (BM) radiation
- * Radiopharmaceutical therapy (e.g., radiolabeled antibody, ^{131}I -metaiodobenzylguanidine [MIBG]): ≥ 42 days after systemically administered radiopharmaceutical therapy
- * Study-specific limitations on prior therapy: small molecule investigational agents: ≥ 14 days or > 5 half-lives must have elapsed from the last dose of the agent, whichever is greater
- Platelet count $\geq 20,000/\text{mm}^3$ (may receive platelet transfusions)
- Hemoglobin ≥ 8.0 g/dL at baseline (may receive red blood cell [RBC] transfusions)
- Creatinine clearance or radioisotope glomerular filtration rate [GFR] ≥ 70 ml/min/1.73 m² or a serum creatinine based on age/gender as follows:
 - * Age: Maximum serum creatinine (mg/dL)
 - ** 2 to < 6 years: 0.8 (male and female)
 - ** 6 to < 10 years: 1 (male and female)
 - ** 10 to < 13 years: 1.2 (male and female)
 - ** 13 to < 16 years: 1.5 (male); 1.4 (female)
 - ** ≥ 16 years: 1.7 (male); 1.4 (female)
- Bilirubin (sum of conjugated + unconjugated) ≤ 1.5 x upper limit of normal (ULN) for age
- Serum glutamate pyruvate transaminase (SGPT) (alanine aminotransferase [ALT]) ≤ 225 U/L. For the purpose of this study, the ULN for SGPT is 45 U/L
- Serum albumin ≥ 2 g/dL
- Left ventricular ejection fraction of $\geq 50\%$ by echocardiogram
- Regulatory Requirements
 - * All patients and/or their parents or legal authorized representatives must sign a written informed consent. Assent, when appropriate, will be obtained according to institutional guidelines
 - * All institutional, Food and Drug Administration (FDA), and National Cancer Institute (NCI) requirements for human studies must be met

Exclusion Criteria

- AML associated with Down syndrome or t(15;17) is not eligible for study
- Pregnant or breast-feeding women will not be entered on this study due to risks of fetal and teratogenic adverse events as seen in animal/human studies. Pregnancy tests must be obtained

in girls who are post-menarchal. Males or females of reproductive potential may not participate unless they have agreed to use an effective contraceptive method for the duration of study therapy and for 2 months after the last dose of enasidenib. Abstinence is an acceptable method of birth control. It is not known if enasidenib is present in breast milk. Breastfeeding is not recommended during therapy or for at least 30 days after the last dose of enasidenib

- Concomitant Medications:
 - * Corticosteroids: Patients receiving corticosteroids who have not been on a stable or decreasing dose of corticosteroid for at least 7 days prior to enrollment are not eligible. If used to modify immune adverse events related to prior therapy, ≥ 14 days must have elapsed since last dose of corticosteroid. The use of corticosteroids to manage the side effect of IDH inhibitor-associated differentiation syndrome (IDH-DS), is permitted on study
 - * Investigational drugs: Patients who are currently receiving another investigational drug are not eligible
 - * Anti-cancer agents: Patients who are currently receiving other anti-cancer agents are not eligible (except leukemia patients receiving hydroxyurea, which may be continued until 24 hours prior to start of protocol therapy; the use of hydroxyurea to manage the side effect of IDH-DS, is permitted on study)
 - * Anti-GVHD agents post-transplant: Patients who are receiving cyclosporine, tacrolimus or other agents to prevent graft-versus-host disease post bone marrow transplant are not eligible for this trial
- Patients must be able to swallow intact tablets whole or use the alternate enasidenib formulation.
 - * Patients with known hypersensitivity to any of the components of enasidenib are not eligible.
 - * Patients with prior exposure to enasidenib or another IDH2 inhibitor are not eligible.
 - * Patients taking the following drugs will be excluded from study entry unless these drugs are discontinued or patients are transferred to a medically acceptable alternative > 5 half-lives before the first dose of enasidenib.
 - ** Drugs with a narrow therapeutic range that are sensitive substrates of the following cytochrome P450 (CYP) enzymes: CYP2C8 (e.g. paclitaxel), 2C9 (e.g. phenytoin and warfarin), 2C19 (e.g. s-mephenytoin), 2D6 (e.g. thioridazine), and 1A2 (e.g. theophylline and tizanidine).
 - ** Breast cancer resistant protein (BCRP) transporter-sensitive substrate rosuvastatin
- Patients with the following leukemia complications are not eligible for this trial:
 - * No intrathecal chemotherapy is permitted on study. Prior to study enrollment, cerebrospinal fluid (CSF) evaluation is only required if there is a clinical suspicion for CNS leukemia. Clinical signs of CNS leukemia (such as facial nerve palsy, brain/eye involvement or hypothalamic syndrome) are not eligible for this trial
 - * Immediately life-threatening, severe complications of leukemia including uncontrolled bleeding, pneumonia with hypoxia or shock, and/or disseminated intravascular coagulation
- Patients who have received a prior solid organ transplantation are not eligible
- Infection: Patients who have an uncontrolled infection or patients with known human immunodeficiency virus (HIV) or active hepatitis B or C are not eligible
- Patients who in the opinion of the investigator may not be able to comply with the safety monitoring requirements of the study are not eligible

Intervention(s)			
Type	Name	Alternate Name	Description
Drug	Enasidenib	1446502-11-9, AG-221, CC-90007 Free Base, ENASIDENIB	Given PO
Drug	Enasidenib Mesylate	1650550-25-6,	Given PO

		2-Methyl-1-[(4-[6-(trifluoromethyl)pyridin-2-yl]-6-{{2-(trifluoromethyl)pyridin-4-yl}amino}-1,3,5-triazin-2-yl)amino]propan-2-ol Methanesulfonate, 2-Propanol, 2-Methyl-1-((4-(6-(trifluoromethyl)-2-pyridinyl)-6-((2-(trifluoromethyl)-4-pyridinyl)amino)-1,3,5-triazin-2-yl)amino)-, Methanesulfonate (1:1), AG-221 Mesylate, CC-90007, ENASIDENIB MESYLATE, Enasidenib Methanesulfonate, Idhifa	
Procedure/Surgery	Bone Marrow Aspiration	Bone Marrow Aspiration, bone marrow aspiration	Undergo bone marrow aspiration
Procedure/Surgery	Bone Marrow Biopsy	Biopsy of Bone Marrow, Biopsy, Bone Marrow, bone marrow biopsy, Bone Marrow Biopsy	Undergo bone marrow biopsy
Procedure/Surgery	Biospecimen Collection	Biological Sample Collection, Biological Sample Collection, Biospecimen Collected, Biospecimen Collection, Specimen Collection	Undergo collection of blood

Arm/Group(s)	
Type	Experimental
Label	Treatment (enasidenib)
Description	Patients receive enasidenib PO QD on days 1-28. Treatment repeats every 28 days for up to 12 cycles in the absence of disease progression or unacceptable toxicity. Patients also undergo bone marrow aspiration and/or biopsy and collection of blood on study.
Intervention(s)	

Type	Name	Alternate Name	Description
Drug	Enasidenib	1446502-11-9, AG-221, CC-90007 Free Base, ENASIDENIB	Given PO
Drug	Enasidenib Mesylate	1650550-25-6, 2-Methyl-1-[(4-[6-(trifluoromethyl)pyridin-2-yl]-6-{{2-(trifluoromethyl)pyridin-4-yl]amino}-1,3,5-triazin-2-yl)amino]propan-2-ol Methanesulfonate, 2-Propanol, 2-Methyl-1-((4-(6-(trifluoromethyl)-2-pyridinyl)-6-((2-(trifluoromethyl)-4-pyridinyl)amino)-1,3,5-triazin-2-yl)amino)-, Methanesulfonate (1:1), AG-221 Mesylate, CC-90007, ENASIDENIB MESYLATE, Enasidenib Methanesulfonate, Idhifa	Given PO
Procedure/Surgery	Bone Marrow Aspiration	Bone Marrow Aspiration, bone marrow aspiration	Undergo bone marrow aspiration
Procedure/Surgery	Bone Marrow Biopsy	Biopsy of Bone Marrow, Biopsy, Bone Marrow, bone marrow biopsy, Bone Marrow Biopsy	Undergo bone marrow biopsy
Procedure/Surgery	Biospecimen Collection	Biological Sample Collection, Biological Sample Collection, Biospecimen Collected, Biospecimen Collection, Specimen Collection	Undergo collection of blood

Primary Outcome Measures		
Title	Description	Time Frame
Incidence of dose limiting toxicities of enasidenib	Frequencies (%) of patients with a dose limiting toxicity stratified by dose level.	Up to 1 year after last dose of study drug
Area under the plasma	A descriptive analysis of the	Up to 120 days

concentration versus time curve of enasidenib	area under the plasma concentration versus time curve of enasidenib including median, minimum and maximum by dose level.	
Total plasma clearance of enasidenib	A descriptive analysis of the total plasma clearance of enasidenib including median, minimum and maximum by dose level.	Up to 120 days
Elimination half-life of enasidenib	A descriptive analysis of the elimination half-life of enasidenib including median, minimum and maximum by dose level.	Up to 120 days
Maximum concentration of enasidenib	A descriptive analysis of the maximum concentration of enasidenib including median, minimum and maximum by dose level.	Up to 120 days

Secondary Outcome Measures		
Title	Description	Time Frame
Plasma 2-HG levels of enasidenib	A descriptive analysis of the plasma 2-HG levels of enasidenib including median, minimum and maximum by dose level.	Up to 120 days
Overall Response Rate of enasidenib	Frequency (%) of patients with at least partial response by dose level.	Up to 2 years
Composite complete remission rate (complete remission [CR]/ CR with incomplete hematologic recovery [CRi])	Will be reported in a table as frequency of response (%) for total overall response rate (ORR) by dose level.	Up to 1 year after last dose of study drug
Time to response of enasidenib	Median time to response with 95% confidence interval.	From the date of first dose to the date of first documented response, assessed up to 1 year after last dose of study drug
Time to complete remission of enasidenib	Median time to remission with 95% confidence interval.	From the date of first dose to the date of first documented CR, assessed up to 1 year after last dose of study drug
Duration of response of enasidenib	Median duration of response with 95% confidence interval.	From the date of first documented response to the

		date of first documented confirmed disease progression/relapse, or death, whichever occurs first, assessed up to 1 year
Duration of complete response of enasidenib	Median duration of remission with 95% confidence interval.	From the date of first documented CR to the date of first documented confirmed disease progression/relapse, or death, whichever occurs first, assessed up to 1 year after last dose of study drug
Event-free survival of enasidenib	Median time to event with 95% confidence interval.	From the date of first dose to the date of documented confirmed disease progression/relapse, or death, whichever occurs first, assessed up to 1 year after last dose of study drug
Overall survival of enasidenib	Median time to death with 95% confidence interval.	From the patient's first dose to the date of the death, or the last date the patient was known to be alive, assessed up to 1 year after last dose of study drug

Markers					
Marker Name	Evaluation Type	Assay Type	Biomarker Use	Biomarker Purpose	Specimen Type
2-HG (2HG; 2-HG; Alpha-Hydroxyglutarate; 2-Hydroxypentanedioic Acid; Alpha-Hydroxyglutaric Acid; Pentanedioic Acid, 2-Hydroxy-; 2-Hydroxyglutaric Acid; 2-Hydroxyglutarate; 2-Hydroxy-Pentanedioic Acid)	Level/Quantity	Unspecified	Integrated	Response Assessment	Blood
Blasts 5-25	Level/Quantity	Unspecified	Integrated	Response	Bone Marrow

Percent of Bone Marrow Nucleated Cells				Assessment	
Blasts More than 5 Percent of Bone Marrow Nucleated Cells (Blasts Greater than 5 Percent of Bone Marrow Nucleated Cells; Blasts Over 5 Percent of Bone Marrow Nucleated Cells)	Level/Quantity	Flow Cytometry	Integral	Eligibility Criterion - Inclusion	Bone Marrow
Blasts Under 5 Percent of Bone Marrow Nucleated Cells (Blasts Less than 5 Percent of Bone Marrow Nucleated Cells)	Level/Quantity	Unspecified	Integrated	Response Assessment	Bone Marrow
Bone Marrow Blasts Decreased by 50 Percent or More Compared to Pretreatment Level (Decrease of Pretreatment Bone Marrow Blast Percentage by at Least 50 Percent; Decrease of Pretreatment Bone Marrow Blast Percentage by at Least 50)	Level/Quantity	Unspecified	Integrated	Response Assessment	Bone Marrow
IDH2 Gene	Genetic	Unspecified	Integral	Eligibility	Blood, Bone

Mutation (Isocitrate Dehydrogenase (NADP(+)) 2, Mitochondrial Gene Mutation; IDH2 Mutation; Isocitrate Dehydrogenase 1 (NADP+), Mitochondrial Gene Mutation)	Analysis			Criterion - Inclusion	Marrow
--	----------	--	--	-----------------------	--------

Participating Sites				
PO ID	Facility	Contact	Recruitment Status & Date(s)	Investigator(s)
66945	Alfred I duPont Hospital for Children, Wilmington, DE 19803 USA	Site Public Contact, email: [contact], [contact]	Active as of 02/01/2023	• [name] - Principal Investigator
29135	Arkansas Children's Hospital, Little Rock, AR 72202-3591 USA	Site Public Contact, email: , [contact]	Active as of 02/01/2023	• [name] - Principal Investigator
133247	C S Mott Children's Hospital, Ann Arbor, MI 48109 USA	Site Public Contact, email: , [contact]	Active as of 02/01/2023	• [name] - Principal Investigator
9858	Centre Hospitalier Universitaire Sainte-Justine, Montreal, Quebec H3T 1C5 CAN	Site Public Contact, email: [contact], [contact]	Temporarily Closed to Accrual as of 08/31/2022	• [name] - Principal Investigator
58509	Children's Hospital Colorado, Aurora, CO 80045 USA	Site Public Contact, email: [contact], [contact]	Active as of 02/01/2023	• [name] - Principal Investigator
25745	Children's Hospital of Alabama, Birmingham, AL 35233 USA	Site Public Contact, email: [contact], [contact]	Active as of 02/01/2023	• [name] - Principal Investigator

196933	Children's Hospital of Pittsburgh of UPMC, Pittsburgh, PA 15224 USA	Site Public Contact, email: [contact], [contact]	Active as of 02/01/2023	• [name] - Principal Investigator
230502	Children's Hospital of San Antonio, San Antonio, TX 78207 USA	Site Public Contact, email: [contact], [contact]	Active as of 05/16/2023	• [name] - Principal Investigator
238382	Children's Hospital of The King's Daughters, Norfolk, VA 23507 USA	Site Public Contact, email: [contact], [contact]	Active as of 02/01/2023	• [name] - Principal Investigator

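### With only 10 patients, is a median with a 95% confidence interval the wrong statistic for the response-time and response-duration outcomes?

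*Protocol*

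**What the plan says.** The Trial Design section describes a single-group study with "Target Enrollment 10". The Secondary Outcome Measures table has nine rows, and four of them concern the timing or duration of response:

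- Time to response: "Median time to response with 95% confidence interval". The clock runs "From the date of first dose to the date of first documented response".
- Time to complete remission: "Median time to remission with 95% confidence interval", also counted from first dose.
- Duration of response: "Median duration of response with 95% confidence interval", counted from the first documented response.
- Duration of complete response: "Median duration of remission with 95% confidence interval", counted from the first documented CR.

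The protocol gives no interval method, no expected response rate, no rule for non-responders in the two time-to rows, and no statement that both limits will be finite. The secondary objective behind these rows is to describe clinical activity.

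**The concern.** Duration of response exists only in patients who respond, and time to response is often summarised in responders alone. With 10 patients enrolled there may be only three to five responders. No distribution-free interval with two finite limits can then reach 95% for a median, because even the full range from smallest to largest value falls short. It would seem that four of the nine secondary outcomes carry a statistic that the design usually cannot supply. A finite interval printed from so few values and labelled 95% would overstate what is known about how quickly and how durably children respond.

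**Working it through.** **Inputs.** Sample size 10 (Trial Design). Median with 95% CI, taken as two-sided (Secondary Outcome Measures). The response rate p is not in the protocol, so a range is assumed. The protocol states no precision or power figure that could be reproduced.

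**Step 1: finite distribution-free interval.** For n uncensored times, the interval from minimum to maximum covers the true median with probability 1 − 2(1/2)^n:

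| n | Minimum to maximum | Minimum to infinity: 1 − (1/2)^n |
|---|---|---|
| 3 | 75.0% | 87.5% |
| 4 | 87.5% | 93.75% |
| 5 | 93.75% | 96.9% |
| 6 | 96.9% | 98.4% |

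Two finite limits therefore need n ≥ 6. An interval open above needs n ≥ 5.

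**Step 2: chance of enough responders.** With X binomial(10, p):

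| Assumed p | P(X ≥ 6) | P(X ≥ 5) |
|---|---|---|
| 0.3 | 4.7% | 15.0% |
| 0.4 | 16.6% | 36.7% |
| 0.5 | 37.7% | 62.3% |
| 0.6 | 63.3% | 83.4% |

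P(X ≥ 6) passes 50% at p of about 0.55. Whether a finite interval is likely or unlikely thus depends wholly on a rate that the protocol does not state. Censored durations lower these chances.

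**Step 3: what the usual method prints.** Brookmeyer-Crowley intervals from a Kaplan-Meier curve were worked out for uncensored samples under the linear, log, log-log and arcsine transforms. For n ≤ 5 none of the four gives a finite upper limit, so the output shows the limit as not reached. It does not show the range of the data as a 95% interval.

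**Step 4: parametric intervals.** Under an exponential model with d events, the limits are 2d/χ²(0.975; 2d) and 2d/χ²(0.025; 2d) times the estimate. At d = 3 they are 0.42 and 4.85 times the estimate. This interval is wide and depends on the model, but it is finite. The need for 6 responders is a property of distribution-free intervals, and the protocol does not commit to one.

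**Step 5: time to response and time to CR.** These rows start at first dose and are not restricted to responders. If all 10 patients are analysed and non-responders are treated as never responding, the exact interval runs from the 2nd to the 9th ordered time. Its coverage is 1 − 2 × (1 + 10)/1024 = 97.9%. That coverage holds even when the 9th time is never observed, because the upper limit is then simply not reached. Likewise, if fewer than half the patients respond, a median reported as not reached is the correct result.

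Nor is a Kaplan-Meier median always undefined with fewer than 5 responders. Suppose 6 non-responders are censored before the first of 4 responses. The curve then falls to 3/4 and next to 2/4, so the median is reached at the second response.

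**The case for a change.** The best case for the concern does not depend on two finite limits. With 4 or fewer responders, even the open interval from the minimum upwards misses 95% for median duration (93.75% at n = 4). The chance of 4 or fewer responders is 85%, 63% and 38% at assumed rates of 30%, 40% and 50%, and it is at least as high for complete responders. Moreover, the statistic is fixed in the protocol's own table, so choosing another distribution-free method later would not cure this. The same table uses median, minimum and maximum for pharmacokinetics and 2-HG. It reports response rates, where an exact interval can always be computed, as frequencies only.

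The arithmetic stands. So does a related point: at these sample sizes the usual Kaplan-Meier intervals can cover less than their nominal level (the linear transform at n = 6 is finite but covers only about 78%). These facts limit how much the duration results can say, but they do not make the table wrong. Naming a median with a confidence interval does not bar reporting limits as not estimable or listing individual durations beside them. The choice of interval is ordinary analysis-plan content. Replacing the interval by minimum and maximum would not clearly improve matters: pharmacokinetic values are fully observed, whereas durations can be censored, and a plain range ignores that. Exact intervals for the response rates would be a reasonable addition, but they would correct nothing that is stated.

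**Conclusion.** The concern does not hold. No figure or rule in the protocol is shown to be wrong or contradictory. The threshold of 6 is correct only for distribution-free intervals with two finite limits, and it follows directly from the table only for the two duration outcomes. Counting any two-finite-limit failure as no interval overstates the problem: at an assumed response rate of 40%, an interval with at least 95% coverage is available with probability about 37% if an open upper limit is accepted, against 17% if it is not. Both figures assume uncensored durations. The feared narrow interval would arise only if someone labelled a minimum-to-maximum range as 95%, which the protocol does not propose and standard Kaplan-Meier output would not do. What is left is imprecision in descriptive secondary outcomes of a 10-patient feasibility study. The conclusion assumes that interval method, censoring and handling of non-estimable limits are left to the analysis plan, as is common.

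### Event-free survival counts only progression/relapse or death, so a patient who never responds and leaves treatment without documented progression keeps adding event-free time

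*Protocol*

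**What the plan says.** Under Secondary Outcome Measures, EFS runs "From the date of first dose to the date of documented confirmed disease progression/relapse, or death, whichever occurs first", assessed until 1 year after the last dose. It is summarised as "Median time to event with 95% confidence interval". Failure to respond, leaving treatment and starting another therapy are not listed as events.

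The Inclusion Criteria require more than 5% "leukemic blasts by morphology and/or flow cytometry in at least one of the following clinical scenarios". The scenarios are second or greater relapse, or "Refractory after ≥ 2 attempts at induction therapy".

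The outline and the arm description give treatment "for up to 12 cycles in the absence of disease progression or unacceptable toxicity". The outline adds: "After completion of study treatment, patients are followed up at 30 days, then periodically up to 1 year".

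The overall response rate (ORR) is defined as "Frequency (%) of patients with at least partial response by dose level", so the protocol already has a threshold that separates responders from non-responders. Target enrolment is 10.

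**The concern.** Nobody is in remission at time zero. For a patient who never remits, relapse cannot happen, which leaves only confirmed progression or death as an event. The protocol uses the same event list for duration of response and duration of complete response. It suits those measures, because their clock starts once the patient is in response. For EFS the clock starts at first dose, with active disease, and the list has no entry for treatment that did not work.

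Treatment can end for toxicity or after 12 cycles (12 × 28 = 336 days, about 11 months) without response and without progression. Such a patient is carried forward as event-free, or is censored as if leaving treatment told us nothing about outcome. Either way the median can be pushed up by failures. A reader who takes EFS in acute leukaemia to include treatment failure would overrate the result.

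**Working it through.** The protocol states no EFS assumption, so there is no figure to reproduce. The check has two parts.

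**1. Can the gap occur on the stated text?**

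- Entry: more than 5% marrow blasts in every patient, so relapse requires a remission first.
- Events: confirmed progression/relapse, or death.
- Stated ends of treatment: progression, unacceptable toxicity, or 12 cycles. Only the first is an EFS event.
- Result: a non-responder who ends by either of the other two routes has no event on that day.

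**2. How far could the median move?**

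From the protocol: N = 10, and follow-up to 1 year after last dose. Everything else is assumed:

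- 4 responders, with events at 5, 7, 9 and 11 months;
- 6 non-responders, of whom k leave treatment at 2 months without progression and 6 − k progress at 3 months.

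The Kaplan-Meier estimate is S(t) = ∏(1 − d/n), and the median is the first time at which S(t) ≤ 0.5. The k patients are handled in three ways: (a) present definition, censored at 2 months; (b) present definition, followed without an event to 2 + 12 = 14 months; (c) counted as an event at 2 months.

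Worked case, k = 3:

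- (a) At 3 months, 7 at risk and 3 events: S = 4/7 = 0.571. At 5 months: 0.571 × 3/4 = 0.429. Median 5.
- (b) At 3 months, 10 at risk and 3 events: S = 0.7. At 5 months 0.6, at 7 months 0.5. Median 7.
- (c) At 2 months S = 0.7. At 3 months: 0.7 × 4/7 = 0.4. Median 3.

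| k | (a) censored at 2 mo | (b) followed to 14 mo | (c) counted as failure |
|---|---|---|---|
| 0 | 3 | 3 | 3 |
| 1 | 3 | 3 | 3 |
| 2 | 3 | 5 | 3 |
| 3 | 5 | 7 | 3 |
| 4 | 5 | 9 | 3 |
| 5 | 7 | 11 | 2 |
| 6 | 7 | not reached | 2 |

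Medians are in months. Several cells rest on S equal to exactly 0.5. With k = 1 under (b), for example, the curve sits at 0.5 from 3 to 5 months, and a midpoint convention would read 4. Differences of that order should not be over-read. The direction does not depend on the convention: in this illustration the present definition never gives a shorter median than (c).

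**The case against.** **The route is narrower than it may seem.** A reader might infer that many patients stop for lack of response within a few months. The protocol names no such reason for stopping. Its stated exits without progression are toxicity and completion of 12 cycles. Assume that 10 to 20% of non-responders leave that way, with an ORR of 40% to 30%. The expected number in 10 patients is then 10 × 0.6 × 0.10 = 0.6 to 10 × 0.7 × 0.20 = 1.4. The binomial chance of at most one is 0.94^10 + 10 × 0.06 × 0.94^9 = 88%, down to 0.86^10 + 10 × 0.14 × 0.86^9 = 58%. One such patient does not move the illustrative median. This stands, and it limits the likely size.

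**Unseen text may close part of the gap.** The document shown does not define progression. If persistent disease counts as progression, fewer patients fall through. A reader might also infer that all time on a later therapy is credited to enasidenib. The document states no rule on censoring at new therapy, and such a rule is commonly left to the analysis plan, so that reading is unsupported.

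**Precision is poor anyway.** With 10 patients and an assumed exponential median of 5 months, the observed median (mean of the 5th and 6th ordered times) has a 95% sampling range of about 2.0 to 10.6 months. This stands, but wide sampling error does not excuse a definition that errs in one direction.

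**A failure event has problems of its own.** Response is assessed up to 1 year after last dose. A patient taken off for toxicity who responds later would be an EFS failure and also a responder in ORR and time to response. In an unmasked study the event also depends partly on the investigator's decision. This argues against replacing the present definition outright.

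**Non-response is already visible** in ORR and the composite complete remission rate. That is true, but it does not correct what the EFS median says.

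**Conclusion.** The concern holds in a limited form. The protocol itself fixes the events, so this is not a detail awaiting the analysis plan. On those events a never-responder who leaves treatment without documented progression has no event at the point of failure, and the median can be lengthened as a result.

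The size cannot be derived from the document. The month figures come from assumed event times and show only that about two or three such patients in 10 are needed to move the median.

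Two stronger readings should be resisted. First, these patients are not event-free for good: progression or death documented up to 1 year after last dose still counts, so the fault is delayed or missed failure. Second, a shift of any particular number of months cannot be claimed, because the share of patients affected, their timing and the definition of progression are all unknown here.

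EFS is a descriptive secondary endpoint in a single-arm study of 10. The primary objectives (safety and pharmacokinetics) are untouched, and the priority is low.

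**What to change.** 1. Keep the present definition, but label it for what it counts: progression/relapse-or-death (progression-free) survival.
2. Report beside it an EFS that adds treatment failure as an event: permanently off enasidenib without having reached at least partial response, or starting other anti-leukaemic therapy without a response, dated on that day. Patients still on drug remain event-free, so slow responders on treatment are not penalised.
3. State how a response first documented after leaving treatment is handled, so that EFS agrees with ORR and time to response.
4. Refer to the definition of progression, and say whether persistent disease meets it.

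The cost is wording and one extra summary line. The off-treatment date and reason should already be collected; the date of any later therapy is needed as well. The downsides are a less favourable EFS figure, and an event that partly reflects investigator decisions in an unmasked study. Showing both versions lets the reader see how far the median depends on uncounted failures.
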